6.2.4 Discontinuation of Adempas[®] Treatment

If the patient discontinues Adempas[®] during the study, the reason for discontinuation will be recorded. Patients should discontinue Adempas[®] treatment if any of the following occur:

- Adverse event(s) where the investigator believes discontinuation of treatment with Adempas[®] is in the best interest of the patient
- Pregnancy

• Any other reason, that in the opinion of the investigator precludes further treatment with Adempas[®].

After discontinuation of treatment with Adempas[®], the follow-up documentation will continue until 30 days after end of therapy.

6.2.5 Withdrawal From the Study

Each patient has the right to refuse further participation in the study at any time and without providing any reasons. A patient's participation is to be terminated immediately upon his/her request. The investigator should seek to obtain the reason and record this on the Case Report Form (CRF). Patients should also be withdrawn from the study for any other reason, that in the opinion of the investigator precludes further participation by the patient.

In this study, withdrawal from the study is independent of the underlying therapy. On the other hand, the follow-up documentation will continue until 30 days after end of therapy.

6.2.6 Replacement

Patients will not be replaced after drop out.

6.2.7 Representativeness

Source population of the present study is patients with PH, specifically PAH and CTEPH. Patients with this rare condition are mostly diagnosed and managed in specialized centers. This includes the initiation and any change of specific drug therapy. The participation of these specialized centers into the registry, the consecutive recruiting of patients and the broad definition of selection criteria is going to ensure the representativeness of the study population.

6.2.8 Visits

The study protocol does not define exact timing of the follow-up visits. The clinical information will be collected, if available and done as per standard of care.

The investigator will document an initial visit, follow-up visits and a final visit for each patient in the case report form (CRF). Follow-up visits in clinical practice usually take place every 3 to 6 months. The CRF will allow for the documentation of visits as performed according to the management of the individual patient.

The final visit is meant to document the end of observation.

Patients will be followed up for an observation period for around 1 year or until end of study (until the last subject has been followed for 1 year) or until 30 days after end of Adempas[®] treatment. The enrollment period to obtain the required 80 patients is expected to be up to 14 months, therefore the study period from FPE to LPLV will be ~26 months.

Enrollment/Initial Visit

Once a patient is found eligible for inclusion, the investigator will inform the patient about the study. This will include discussing the consent form and asking the patient to read and – when agreeing to participate – sign the informed consent.

For patients in Bayer studies PATENT 2 and CHEST 2, their eligibility for EXPERT-China study will be evaluated after the completion of the Termination Visit and the Safety Follow-up Visit 30 days later in BAY 11349/12935.

The following information will be collected (details in Section 6.3):

- Patient demographics
- Medical history
- Comorbidity
- Adverse events
- PH etiology according to Nice Classification 2013 and disease history
- Pregnancy status
- History of smoking
- 6-minute walking distance*
- WHO FC*
- Borg dyspnea index*
- EQ5D VAS*
- Lung function*, Cardiac rhythm
- Hemodynamic parameters from right heart catheter measurement*
- Biomarkers (NT-proBNP, BNP) *
- Laboratory tests*
- Systemic BP before start of Adempas[®]
- Treatment:
 - o Relevant prior and concomitant medication
 - o PAH-specific drugs or Adempas®
- Resource use

*if available and done as per standard of care

Follow-up Visits During Treatment

Follow-up examinations in clinical routine usually take place every 3 to 6 months. The CRF will allow for visits to be documented according to the management of the individual patient. At each of these visits the following will be documented:

- Adverse events
- Changes of treatment
- Changes regarding demographics, pregnancy, smoking
- 6-minute walking distance*
- WHO FC*
- Borg dyspnea index*
- EQ5D VAS*
- Lung function*, Cardiac rhythm,
- Hemodynamic parameters from right heart catheter measurement *
- Biomarkers (NT-proBNP, BNP) *
- Laboratory tests*
- Resource use

*if available and done as per standard of care

Final Visit and End of Observation Period

The final data collection (last visit) is 30 days after discontinuation of therapy or at end of study (whichever is earlier). At this final observation point, the patient's condition and a treatment assessment will be documented as at the follow-up visits with additional information on:

- Regular end of observation, or
- Discontinuation of therapy /Withdrawal from study
- Reason for discontinuation/withdrawal, i.e.: patient failed to follow up, patient decision, investigator decision, pregnancy, insufficient/no treatment effect, unexpected strong treatment effect, (suspected) drug interaction, SAE (must be reported **immediately**), death (date and relation to disease or treatment), therapy change (which therapy and reason for switch), center closed, study termination

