6.7.4 Analysis of Secondary Outcome(s)

The secondary safety outcomes will be analyzed similar to the primary outcomes. Subgroup analyses will be conducted for selected secondary endpoints (e.g. 6-minute walk test, WHO FC, hospitalization).

Analyses of adverse events will be conducted for PH subgroups (e.g., inoperable vs. postsurgery CTEPH patients, monotherapy vs. combination therapy PAH patients).

For the effectiveness variables, summary statistics and changes form baseline will be calculated for

- 6-minute walking test
- Borg dyspnea index
- EQ5D VAS
- Hemodynamic measurements
- Biomarkers

WHO FC will be analyzed by frequency tables including changes from baseline.

The variables of hospitalization due to PH and drug utilization (reason for drug switch or interruption or discontinuation of Adempas[®]) will be analyzed by frequency tables and summary statistics.

32

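### The final-visit list of reasons for stopping has a code for a serious adverse event but none for a non-serious one, and does not match Sections 6.2.4 and 6.3.16

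*Protocol*

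**What the plan says.** Section 6.2.4 says of a patient who stops the drug that "the reason for discontinuation will be recorded". The first ground it gives is "Adverse event(s) where the investigator believes discontinuation of treatment with Adempas" is judged to be in the patient's best interest. No seriousness limit is attached. Pregnancy and a general investigator-judgement clause follow.

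Section 6.2.8, on the final visit, sets out the reasons to be recorded, introduced by 'i.e.': "patient failed to follow up, patient decision, investigator decision, pregnancy, insufficient/no treatment effect, unexpected strong treatment effect, (suspected) drug interaction, SAE". The last of these must be reported at once. The list closes with "death (date and relation to disease or treatment), therapy change (which therapy and reason for switch), center closed, study termination".

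Section 6.3.16 asks for a reason whenever a relevant drug is changed. It names efficacy or tolerability (in one phrase), the patient's request, and administrative reasons.

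Section 6.3.2 makes switch, interruption or discontinuation of the drug, with its reason, part of the secondary drug-use variable. Section 6.7.4 plans frequency tables and summary statistics for the "reason for drug switch or interruption or discontinuation of" the drug.

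**The concern.** The abbreviation that introduces the Section 6.2.8 list means 'that is', so the list reads as complete. Pregnancy, the second ground in Section 6.2.4, has its own code. The first ground, an adverse event, has one only if the event is serious.

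Two sites could therefore code the same clinical situation differently, and neither could code it as an adverse event. The error runs one way: in this field, stops related to adverse events can be undercounted, while headings such as patient decision or investigator decision absorb them. The registry's primary objective is long-term safety, and Section 6.7.6 itself names misclassification as a possible source of bias. The reason for stopping is only a secondary descriptive variable, but it is a natural place to look for tolerability.

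**Working it through.** The protocol gives no discontinuation rate and no figure to reproduce, so the check sets the sections side by side.

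**Step 1: items in the Section 6.2.8 list.** There are twelve: lost to follow-up, patient decision, investigator decision, pregnancy, insufficient effect, unexpectedly strong effect, suspected drug interaction, SAE, death, therapy change, centre closed, study termination. None is a non-serious adverse event, intolerance or 'other'.

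**Step 2: Section 6.2.4 against that list.**

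| Ground for stopping in 6.2.4 | Code in 6.2.8 |
|---|---|
| Adverse event, serious | SAE |
| Adverse event, non-serious | none |
| Pregnancy | pregnancy |
| Any other reason in the investigator's opinion | investigator decision, or a more specific item |

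**Step 3: where a non-serious event would go.** A stop for non-serious symptomatic hypotension could be filed as patient decision, investigator decision, unexpectedly strong effect or, if another drug is started, therapy change. A stop for non-serious haemoptysis could go under the same headings except, most plausibly, the strong-effect one. Section 6.3.2 lists both as events of interest, and explicitly covers haemoptysis and pulmonary haemorrhage whether serious or not.

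**Step 4: other records of the same fact.**

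- Section 9.1.2 requires seriousness, relationship to the drug and action taken for every adverse event.
- Section 6.3.16 requires start and stop dates and a reason for change that mentions tolerability. Its wording can be read as joining tolerability with lack of efficacy in one item, so it may not isolate tolerability. It also speaks of change rather than discontinuation.
- The therapy-change item in 6.2.8 asks for the reason for the switch, which helps only for patients who switch.

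**Step 5: source of the table.** Section 6.7.4 does not name a field. Its wording follows the drug-use variable in Section 6.3.2 and includes interruption, for which the final-visit list has no item. The final-visit field therefore cannot be the only source, but it is a candidate for the discontinuation part.

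**Step 6: scale.** With the planned 80 patients (Section 6.5) as denominator, one misfiled patient moves a category by 1/80 = 0.0125, or 1.25 percentage points. If the table is instead expressed per patient who stopped, each misfiled patient weighs more, but that denominator is unknown.

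**The case against.** The strongest reply is that the information is collected anyway. Action taken is documented for every adverse event, so stops due to adverse events can be counted from the adverse event form, and the medication record gives a second route. The choice of source for a frequency table is ordinary content for the SAP, and the detailed code list may sit in the CRF completion guidance; neither is shown. The primary endpoints, incidence of adverse and serious adverse events and all-cause mortality, do not use the reason field.

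Most of this stands. A reader might infer that tolerability stops are lost to the study, or that the planned table will show no stops for non-serious events whatever happens. The protocol does not support either inference: it does not tie the table to the final-visit field, and other records can hold the missing information.

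The reply does not remove the mismatch itself. The list is stated in the protocol as complete and disagrees with Section 6.2.4. An SAP cannot tabulate from that field a category that the field never offered. The other routes do not share a common code list, and the protocol states no reconciliation between them, so one patient could appear as an investigator decision in one record and as withdrawn for an adverse event in another.

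**Conclusion.** The point holds as an inconsistency in what is collected. Followed as written, the final-visit field files every stop for a non-serious adverse event under another heading, and any discontinuation-reason table built from that field would understate stops related to adverse events. This rests on two readings: that the list is exhaustive as its introduction implies, and that the CRF follows it.

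It does not follow that such stops are understated in the study's results as a whole; that depends on which field is used, which the protocol leaves open. The size of any understatement cannot be computed from the document, beyond 1.25 percentage points per misfiled patient with 80 as denominator. The effect is confined to a secondary descriptive variable. Severity is low to moderate.

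**What to change.** Reconcile the reason lists in Sections 6.2.4, 6.2.8 and 6.3.16 so that they use one set of categories. In Section 6.2.8, replace the single serious-event item with two: adverse event, serious (report immediately), and adverse event, non-serious. Link each to the adverse event record. Name the field that supplies the discontinuation-reason table, and check the reason field against action taken on the adverse event form before database lock.

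This concerns only how a stop is recorded, not when treatment should stop. The cost is one added CRF code, one edit check and a wording change. It adds no visit or procedure, so the observational character of the registry is unchanged.

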6.3 Variables

The investigator collects historic data (demographic and clinical characteristics) from medical records if available, or else by interviewing the patient. Likewise, the investigator collects treatment related data during the initial visit and follow-up visits based on assessments that are performed routinely. The investigator documents the study-relevant data for each patient in the case report form (CRF).

Variables	Initial visit	Follow-up visit(s)	Final visit
Demographics	Х	X	Х
Medical history	Х		
Concomitant disease	Х	X	Х
Adverse Events**	Х	X	Х
PH etiology	Х		
Pregnancy status	Х	X	Х
Smoking history/status	Х	X	Х
Systemic BP before start of Adempas [®]	Х		
6-minute walk test*	Х	X	Х
WHO FC*	Х	X	Х
Borg dyspnea index*	Х	X	Х
EQ5D VAS*	Х	X	Х
Hemodynamic measurements, lung function, cardiac rhythm*	Х	X	Х
Biomarkers*	Х	X	Х
Laboratory tests*	Х	X	Х
Treatment medication	Х	X	Х
Concomitant medication	Х	X	Х
Resource use in hospital and outpatient care	Х	X	Х

 Table 1
 Tabulated overview on variables collected during the study

* If data available and done as per standard of care

**Serious Adverse Events must be reported to Bayer within 24 hours.

6.3.1 Variables to Determine the Primary Endpoint(s)

The variables for primary objective are:

- Adverse events (AE) and serious adverse events (SAE)
- All-cause mortality

6.3.2 Variables to Determine the Secondary Endpoints

The outcome variables for secondary objectives are:

- AE and SAE in the different PH indications (PAH, CTEPH)
- Adverse events of interest
 - o Symptomatic Hypotension (date BP measurement, symptoms)
 - o Haemoptysis and pulmonary haemorrhage (serious and non-serious).

Specific information regarding relevant history, current condition, diagnostics, treatment, specific lab values and outcome to be documented in a specific CRF section in case AE/SAE of interest occurred

- Measurements of clinical effect
 - o 6-minute walk test
 - o WHO FC
 - o Borg dyspnoea index
 - o EQ5D VAS
 - o Haemodynamic parameters from right heart catheter measurement
 - o Biomarkers
- Resource use

o Hospitalization (due to PH or other reason, emergency admission, intensive care unit, number of days)

- o Outpatient visits at PH centre
- o Home care (nurse, days per week, hours per day)
- o Drug use, including switch or interruption or discontinuation of Adempas[®] and associated reason

6.3.3 Demographics

For demographic/socio-demographic assessment, the following data will be recorded:

- Year of birth
- Sex

MK-4836-001-01 FINAL PROTOCOL

• Height and Weight

6.3.4 Co-morbidities (medical history, concomitant diseases)

Co-morbidities are any medical findings, whether they pertain to the study indication, that were present before start of therapy with Adempas[®], independent of whether they are still present.

Findings meeting the criteria listed below are relevant to the study indication and should be documented if collected as part of routine clinical practice:

• Date of first PH diagnosis (month/year)

• Aetiology of PH according to Nice Classification 2013, subgroups of CTEPH (inoperable, post-surgery), subgroups of PAH (monotherapy, combination therapy)

- Relevant concomitant diseases (e.g. vascular disease, diabetes, cancer)
 - Date of diagnosis

• History of haemoptysis (date frequency, severity, bronchial arterial embolization (BAE), other pulmonary disease, trauma)

- Hepatic impairment (no/yes)
 - o Child-Pugh classification
- Renal impairment (no/yes)
 - o Severity
 - o Estimated Glomerular filtration rate by Cockroft-Gault formula

For any comorbidity, the specific diagnosis as well as start and stop dates/ongoing must be documented.

Proprietary

6.3.5 Pregnancy

• Pregnancy Monitoring Form

6.3.6 Smoking

- Smoking history
- Current status

6.3.7 6-minute Walk Test (if available)

- Date
- Distance

6.3.8 WHO Functional Class (if available)

- Date
- Result

6.3.9 Borg Dyspnoea Index (if available)

- Date
- Result

6.3.10 EQ5D Visual Analog Scale (if available)

- Date
- Score

6.3.11 Haemodynamic Measurements (if available)

- Date
- Mean pulmonary arterial pressure (mPAP, mmHg)
- Pulmonary vascular resistance (dyn*sec*cm⁻⁵)
- Pulmonary capillary wedge pressure (PCWP, mmHg)
- Right atrial pressure (RAP, mmHg)
- Cardiac index (L/min/m²)

6.3.12 Cardiac Rhythm (if available)

- Date
- Normal sinus rhythm, atrial fibrillation, atrial flutter or other arrhythmia

6.3.13 Lung Function (if available)

- Date
- TLC, FVC, FEV1, DLCO, PaO₂, PaCO₂, O₂ BGA

6.3.14 Biomarkers (if available)

- Date
- Brain Natriuretic Peptide (BNP; pg/mg or pmol/l)
- NT-pro BNP (N-terminal pro Brain Natiruretic Peptide, pg/mg or pmol/l)

6.3.15 Laboratory Tests (if available)

• Date

- Haemoglobin
- Haematocrit
- INR (if on VKA treatment)
- Creatinine
- Transaminases (ALT/AST)

Additional laboratory tests for CHD patients only

- Date
- Uric acid
- Sodium
- Iron, Ferritin, Transferrin, Soluble transferrin receptor, sTfR-ferritin index
- C-reactive protein
- MCV, MCH, MCHC
- Homocysteine

6.3.16 Prior and Concomitant Medication

All medication taken before study start (initiated and stopped before study start) is termed prior medication. All medication taken in addition (either initiated before study start or during the study) is termed concomitant medication.

Prior and concomitant medication meeting the criteria listed below are considered to be relevant and must be documented:

- PH/PAH-specific therapy
 - o Adempas®
 - o ERA
 - Bosentan
 - Ambrisentan

o PDE-5 inhibitors (physician will be alerted that the combination of PDE5 inhibitors with Adempas[®] is contraindicated)

o Nitrates or nitric oxide donors (physician will be alerted that the combination of PDE5 inhibitors with Adempas[®] is contraindicated)

- o Prostacyclins
 - Epoprostenol
 - Treprostinil
 - Iloprost

- Beraprost
- o Other specific targeted therapy: calcium channel blocker
- o Oral anticoagulation
 - Vitamin K antagonists
 - Other
- Other medications (only CHD: other cardiovascular drugs, antiplatelets)

Information to be documented includes:

- Trade name and INN
- Start and stop date
- Date of dose change, switch or addition of a specific drug/Adempas[®]
- Reason for change (lack of efficacy or tolerability, patient's request, administrative)
- Dose
- Unit
- Frequency
- Administration mode
- Indication

Additional information on Adempas[®] to be documented includes:

- Individual dose after initial dose adjustment period
- BP before the 1st administration

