6.1.3 Strengths of Study Design

In this therapeutic area a multicenter exposure registry with a mix of patients previously enrolled in two Bayer Phase III clinical trials with riociguat and patients newly starting Adempas[®] allows for a structured prospective documentation of long-term data on safety, clinical effect, and information on how Adempas[®] is used by PH experts. As Adempas[®] is the first sGC-stimulator in clinical use and all available clinical data in Chinese patients derive from well-defined clinical studies, this registry may collect additional data on important potential safety risks, drug interactions and missing information.

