6.2.3 Exclusion Criterion/Criteria

• Patients currently participating in an interventional clinical trial (If a patient is currently in the CHEST or PATENT (riociguat) long term extension trials, then the patient can be considered for transition into EXPERT China study after the last dosing of riociguat.)

- Female patient who is pregnant
- Patients with severe hepatic impairment (Child Pugh grade C)
- Patients with SBP<95 mmHg when newly treated with Adempas[®]
- Patients who have been diagnosed with idiopathic interstitial pneumonia
- Co-administration with specific PDE 5 inhibitors (such as sildenafil, tadalafil or vardenafil) or nonspecific PDE 5 inhibitors (such as dipyridamole or theophylline) (see Section 6.3.16).
- Co-administration with nitrates or nitric oxide donors (such as amyl nitrite) in any form (see Section 6.3.16).
- Any condition which, in the opinion of the investigator may confound the results or result in unwarranted risk in administering Adempas[®] to the patient.

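### Section 6.3.16 puts the PDE5-inhibitor alert on the nitrate entry, omits the non-specific PDE inhibitors that 6.2.3 refers to it, and limits antiplatelet and other cardiovascular drug recording to CHD patients

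*Protocol*

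**What the plan says.** Protocol 6.2.3 excludes three groups of co-medication and refers to 6.3.16 each time. The first is specific PDE 5 inhibitors. The second, in the same bullet, is "nonspecific PDE 5 inhibitors (such as dipyridamole or theophylline) (see Section 6.3.16"). The third is "Co-administration with nitrates or nitric oxide donors (such as amyl nitrite) in any form (see Section 6.3.16").

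Protocol 6.3.16 sets the recording duty: "Prior and concomitant medication meeting the criteria listed below are considered to be relevant and must be documented". The list beneath it has:

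- an entry "PDE-5 inhibitors (physician will be alerted that the combination of PDE5 inhibitors with" Adempas is contraindicated);
- an entry "Nitrates or nitric oxide donors (physician will be alerted that the combination of PDE5 inhibitors with" Adempas is contraindicated);
- ERAs, prostacyclins, calcium channel blockers and oral anticoagulants (vitamin K antagonists and others);
- "Other medications (only CHD: other cardiovascular drugs, antiplatelets").

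Section 6.3.2 makes symptomatic hypotension, and haemoptysis with pulmonary haemorrhage, the adverse events of interest. It adds a dedicated CRF section, completed when such an event occurs. Section 6.7.3 gives concomitant medication use and baseline systolic blood pressure as example subgroups for the safety analysis, if numbers allow. Section 6.1.3 says that "this registry may collect additional data on important potential safety risks, drug interactions and missing information".

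**The concern.** Section 6.2.3 relies on 6.3.16 to carry the excluded classes, and on two of the three it does not. An eCRF built from 6.3.16 as written would show a warning about PDE5 inhibitors to a physician entering a nitrate. It would also give no explicit prompt or duty to record dipyridamole or theophylline.

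The CHD restriction is a different kind of problem. Drugs that can lower blood pressure or affect bleeding are natural covariates for the two events of interest. If a drug is not recorded in patients without an event, no later analysis plan can recover its exposure. This is therefore a matter for the protocol and not something left to the SAP.

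**Working it through.** The protocol states no figure on this point, so the check sets the sections side by side.

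**Step 1: excluded classes against the list they are referred to.**

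| Class excluded in 6.2.3 | Named in 6.3.16? | Alert in 6.3.16 names that class? |
|---|---|---|
| Specific PDE5 inhibitors | Yes | Yes |
| Nitrates / nitric oxide donors | Yes | No, it names PDE5 inhibitors |
| Dipyridamole, theophylline (non-specific) | No | No entry of their own |

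One of the three classes is handled consistently. The third is ambiguous: because 6.2.3 labels these drugs non-specific PDE 5 inhibitors, a site might place them under the PDE-5 line. Another site might not, since neither the drugs nor the non-specific class is mentioned and the duty covers only what is listed.

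**Step 2: who has which co-medication recorded (6.3.16).**

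| Drug group | Recorded for |
|---|---|
| PDE5 inhibitors, nitrates / NO donors | All patients |
| ERAs, prostacyclins, calcium channel blockers | All patients |
| Oral anticoagulants | All patients (with INR if available and on a vitamin K antagonist, 6.3.15) |
| Other cardiovascular drugs, antiplatelets | CHD patients only |

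**Step 3: what a rate by drug use needs.** Section 6.7.3 defines the incidence proportion as patients with the event divided by treated patients, and the incidence rate as patients with the event divided by person-years on treatment. For users of a given drug these become:

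- proportion = (users with event) / (users with event + users without event)
- rate = (users with event) / (person-years among users)

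For a drug in the last row of Step 2, in a CTEPH or non-CHD PAH patient, the only possible source is the event-specific CRF section. It is opened only when an event of interest has occurred, so it can supply the numerator at most. Users without an event, and their person-years, are not collected, so neither quantity can be formed. For the drugs in the first three rows both can be.

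**Step 4: how many patients.** Planned enrolment is at least 80 (6.5). If k of 80 patients have CHD, 80 − k have no required record of these drugs. The protocol gives no expected k; the upper limit, at k = 0, is all 80.

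**Step 5: blood pressure.** Table 1 lists "Systemic BP before start of Adempas" at the initial visit only, and 6.3.16 asks for the value before the first administration. Section 6.3.2 asks for a measurement at symptomatic hypotension. For patients already on treatment at enrolment, the text does not say whether the start means the first-ever dose or the first dose after enrolment.

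**The case against.** The strongest reply is that little is lost. Nitrates and PDE5 inhibitors are separate must-document entries with dose and dates, so a misworded alert removes no data. Co-administration is an exclusion, label-prohibited drugs are not allowed (7.5), and off-label use, medication error and misuse must be reported if the investigator becomes aware of them (9.2.5). The subgroups in 6.7.3 are examples, conditional on numbers. The drug-interaction statement in 6.1.3 says only that the registry may collect such data. This is a descriptive registry of about 80 patients, and field-level detail belongs to the CRF and the data management plan, which are not shown.

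Most of this stands, and it rules out several stronger readings:

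- A reader might infer that contraindicated use would go undetected. The documents do not support this for nitrates or PDE5 inhibitors. For the non-specific PDE inhibitors the gap is the lack of an explicit recording duty, which does not mean their use could never come to light.
- A reader might infer that stratification by concomitant medication is impossible. It remains possible for every drug group recorded for all patients, including anticoagulants.
- A reader might infer that the absence of routine follow-up blood pressure undermines the hypotension analysis. The event of interest is symptomatic hypotension, blood pressure is collected when it occurs, and no blood-pressure-change endpoint is planned in 6.1.2.
- A reader might want baseline systolic pressure set to the enrolment value for everyone. That would mix pre-treatment values in newly treated patients with on-treatment values in those already treated.

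The reply does not remove the mismatch between 6.2.3 and 6.3.16, which is in the current protocol text. Nor does it answer the CHD limit: whatever the event-specific CRF section records, it covers cases only.

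**Conclusion.** The point holds in a limited form. Two inconsistencies are certain on the face of the protocol: the nitrate alert names the wrong class, and the reference from 6.2.3 to 6.3.16 for dipyridamole and theophylline leads to a list that names neither. They are operative, because sites and eCRF builders work from that list.

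The CHD-only limit is the natural reading of the entry. On that reading, hypotension and haemoptysis rates by use of antiplatelets or other cardiovascular drugs cannot be calculated for CTEPH and non-CHD PAH patients. That narrows one example subgroup analysis in 6.7.3. It does not touch the primary endpoints or stratification by the drugs recorded for all.

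The conclusion assumes that the eCRF follows 6.3.16 as written and asks no more than the protocol does. On blood pressure, the most the text supports is a request for clarification. The point is worth correcting because the change is nearly free, but it does not threaten the study.

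**What to change.** 1. Reconcile 6.3.16 with 6.2.3 so that each alert names the class being entered. The clinical content of the alert is for the sponsor to settle; no rule is proposed here.
2. Name the excluded non-specific PDE inhibitors in the must-document list of 6.3.16, and use one label for the class in both sections.
3. Record antiplatelets and other cardiovascular drugs for all patients, from routine records, by removing the CHD restriction on that entry.
4. At most, state whether blood pressure before the start of Adempas means before the first-ever dose or before the first dose after enrolment for patients already on treatment.

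Items 1, 2 and 4 are edits to protocol and eCRF text. Item 3 costs slightly more data entry per patient. No visit, test or procedure is added, so the observational character described in 6.1 is unchanged.
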